6.3.4. Electrocardiograms

Average of the triplicate measurements (where applicable) will be used in analyses. Absolute values and changes from baseline in QT, heart rate, QTcF, PR and QRS will be summarized by treatment group and time point using sponsor reporting standards. Tables will be paged by parameter.

Mean changes from baseline in QT, heart rate and QTcF will be plotted against time point. On each plot there will be 1 line for each treatment group with all treatments included on the same plot including placebo.

MMRM models (as described in Section 5.2.3) will be applied to the change from baseline at Weeks 2, 4, 6, 8, 10, 12, 16, 18, 22 and 26 for Cohorts 1 & 2 and at Weeks 4, 8, 12, 16, 20, 24, 28 and 32 for Cohort 3 separately, for QT, heart rate and QTcF separately using the safety analysis set (as defined in Section 4). From each model, the LSMeans together with 90% confidence intervals, standard errors and p-values will be obtained for each treatment group at each time point. Differences in LSMeans between each treatment group of danuglipron relative to placebo at each time point, together with 90% confidence intervals, standard errors and 2-sided p-values will also be obtained. A plot of the LSMean differences to Placebo (including 90% confidence intervals) over time, with a separate line for each treatment group of danuglipron will be produced separately for each parameter. Standard SAS outputs will be provided to support the main statistical summary tables but will not be included in the CSR.

PFIZER CONFIDENTIAL DMB02-GSOP-RF02 8.0 Statistical Analysis Plan Template TMF Doc ID: 98.03 Page 39 of 61 ECG endpoints and changes from baseline (QTcF, PR and QRS) will also be summarized descriptively by treatment group and overall using categories as defined in the Appendix 4 (for QTc these correspond to the Pfizer Guidance¹⁰). Numbers and percentages of participants meeting the categorical criteria will be provided. All planned and unplanned post-dose time points will be counted in these categorical summaries. All values meeting the criteria of potential clinical concern will be listed.

Maximum absolute value (post-dose) and the maximum increase from baseline for QTcF, PR and QRS will be summarized by treatment group according to sponsor reporting standards.

Listings of participants with any single post-dose value > 500 msec will also be produced for QTcF.

6.3.5. Assessment of mental health as determined by C-SSRS and PHQ-9.

Screening, baseline and post-baseline C-SSRS data (mapped to C-CASA scores as described in Section3.2.2.3) using the safety population defined in Section 4, will be separately summarized categorically by treatment group and time point as outlined in Section 5.2.2.

Baseline and post-baseline PHQ-9 data (responses to each of the 9 items) using the safety population defined in Section 4 will be summarized categorically for each question separately by treatment group and time point as outlined in Section 5.2.2. The PHQ-9 total score as defined in Section 3.2.4 will additionally be summarized descriptively by treatment group and time point as outlined in Section 5.2.1.

The number of participants who met the criteria for referral to a mental health professional will be listed and summarized by treatment group and time point as outlined in Section 5.2.2.

6.4. Other Endpoint(s) (or, Exploratory Endpoint[s])

6.4.1. Trough plasma concentrations of danuglipron at time points specified in the SoA

Danuglipron concentrations will be characterized by C_{trough} and will be summarized by treatment group and by time point using the following descriptive statistics: number of participants contributing at each time point, arithmetic mean, median, minimum, maximum, Q1, Q3, standard deviation, geometric mean, and geometric CV (%).

Median C_{trough} versus time point will be plotted by treatment group including error bars representing the inter-quartile range (i.e. Q1 to Q3).

C_{trough} values from PK samples that were collected after discontinuation of investigational product will be listed but excluded from summarization.

The post-dose random plasma concentration data will only be listed (and not summarized); these data are noted for use in supplemental population-PK analyses.

In addition, as permitted by data and determined by the sponsor, PK-PD relationship between plasma concentrations of danuglipron and effect on primary, secondary and tertiary endpoints may be characterized using a population PK-PD approach. The objective of such an analysis, if conducted, would aim to explore potential demographic determinants (eg, age, gender, and weight) influencing the observed PK or PD variability in response to danuglipron. The population PK-PD analysis, if conducted, will be reported separately from the main CSR.

6.4.2. CFB in fasting plasma insulin, HOMA-IR and HOMA-B at Weeks 4, 8, 12, 16, 22 and 26

In all cases a dataset similar to Estimand Set 1 as specified in Section 4 will be utilised.

Absolute changes from baseline in fasting plasma insulin, HOMA-IR and HOMA-B will be summarised and analysed separately similar to body weight in Section 6.1.1.1, including follow-up, where HOMA-IR and HOMA-B are as defined in Section 3.2.2.

MMRM models (as described in Section 5.2.3) will be applied to each parameter separately, where each will include the absolute change from baseline at Weeks 4, 8, 12, 16, 22 and 26 for Cohorts 1 & 2 and at Weeks 4, 8, 12, 16, 20, 24, 28 and 32 for Cohort 3 separately, and the baseline term will be the baseline for the associated parameter. Results similar to body weight in Section 6.1.1.1, where back-transformation of LSMeans and LSMean differences will not be applicable, will be reported separately along with standard SAS output (where the latter will not be included in the CSR).

6.4.3. Absolute CFB in waist circumference over time.

In all cases a dataset similar to Estimand Set 1 as specified in Section 4 will be utilised.

CFB in waist circumference will be summarized at Weeks 2, 4, 6, 8, 10, 12, 16, 18 and 22 for Cohorts 1 & 2, and at Weeks 4, 8, 12, 16, 20, 24 and 28 for Cohort 3 separately. Summary and analysis results will be reported as described in Section 6.2.3.

6.4.4. Absolute CFB in waist-to-hip ratio over time

In all cases a dataset similar to Estimand Set 1 as specified in Section 4 will be utilised.

CFB in waist-to-hip ratio will be summarized at Weeks 2, 4, 6, 8, 10, 12, 16, 18 and 22 for Cohorts 1 & 2 and at Weeks 4, 8, 12, 16, 20, 24 and 28 for Cohort 3 separately. Summary and analysis results will be reported as described in Section 6.2.4.

6.4.5. Shift from baseline in glycemic category (normoglycemia, pre-diabetes, or T2DM) at End of Treatment

In all cases a dataset similar to Estimand Set 1 as specified in Section 4 will be utilised.

A shift table for the baseline glycemic category to the End of Treatment glycemic category will be presented by treatment group.

6.4.6. CFB in systolic and diastolic BP over time

In all cases a dataset similar to Estimand Set 1 as specified in Section 4 will be utilised.

Absolute and change from baseline in systolic and diastolic blood pressure will be summarised descriptively and analyzed as described in Section 6.3.3 at Weeks 2, 4, 6, 8,

10, 12, 16, 18, 22 and 26 for Cohorts 1 & 2 and at Weeks 4, 8, 12, 16, 20, 24, 28 and 32 for Cohort 3 separately.

6.4.7. CFB in lipid parameters over time

In all cases a dataset similar to Estimand Set 1 as specified in Section 4 will be utilised.

Absolute and change from baseline in lipid parameters will be summarised descriptively and analyzed as described in Section 6.3.2.1 at Weeks 2, 4, 6, 8, 10, 12, 16, 18, 22 and 26 for Cohorts 1 & 2 and at Weeks 4, 8, 12, 16, 20, 24, 28 and 32 for Cohort 3 separately.

6.4.8. CFB in SF-36v2® subscales and summary scores

In all cases a dataset similar to Estimand Set 1 as specified in Section 4 will be utilised.

Absolute and change from baseline in the 11 SF-36v2 transformed norm-based T-scores (covering 8 domains, health transition and 2 components) will be summarised descriptively by treatment group and time point as described in Section 5.2.1, at Weeks 16 and 26 for Cohorts 1 & 2 and at Weeks 16, 24 and 32 at Cohort 3 separately.

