- CFB in SF-36v2® subscales and summary scores at:
 - \circ Weeks 16 and 26 at Weeks 16 and 26 for Cohorts 1 and 2.
 - Weeks 16, 24 and 32 for Cohort 3.

The SF-36v2®^{3,4} is a 36-item questionnaire that measures functional health and well-being from a patient's perspective. It is a generic questionnaire and can be used across age (adults), disease, and treatment groups. The questionnaire consists of 8 health domain scales: physical functioning (10 items), role-physical (4 items), bodily pain (2 items), general health (5 items), vitality (4 items), social functioning (2 items), role-emotional (3 items), mental health (5 items), reported health transition (1 item) and 2, physical and mental component summary scores. Each health domain scale raw score is transformed to 0-100 scale which can then be converted to norm-based T-scores (Mean=50, SD=10).

The following transformed norm-based T-scores will be derived: physical functioning (PF); role-physical (RP); bodily pain (BP); general health (GH); vitality (VT); social functioning (SF); role-emotional (RE); mental health (MH); reported health transition; physical component summary (PCS); and mental component summary scores (MCS).

PFIZER CONFIDENTIAL DMB02-GSOP-RF02 8.0 Statistical Analysis Plan Template TMF Doc ID: 98.03 Page 22 of 61

- CFB in Eating-Related Factors Daily Diary at:
 - Weeks 4, 8, 12, 16, 22 and 26 for Cohorts 1 and 2.
 - Weeks 4, 8, 12, 16, 20, 24, 28 and 32 for Cohort 3.

The Eating-Related Factors Daily Diary is a daily, self-administered questionnaire that measures eating-related factors. The diary consists of 5 items that ask participants to evaluate their hunger, appetite, fullness, and cravings in the past 24 hours.

At baseline and at the timepoints listed above, the 7-day average score will be calculated separately for each item. This average score will be based on the 7 days leading up to the respective week (i.e. for Week 4 it would be Day 22 up to Day 28) and will be considered missing when 4 or more days are missing in a 7 day period. Baseline is defined as the 7 days leading up to dosing on Day 1 (i.e. Day -7 up to and including Day -1). The change from baseline for each post-dose time point will then be calculated for each of the 5 items separately.

• CFB in PGI-S at each planned in-clinic study visit up through the End of Treatment visit.

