6.4.14. PGI-C

In all cases a dataset similar to Estimand Set 1 as specified in Section 4 will be utilised.

PGI-C data will be summarized categorically by treatment group and time point for each item as described in Section 5.2.2, at Weeks 4, 16 and 26 for Cohorts 1 & 2 and at Weeks 4, 16, 24 and 32 for Cohort 3 separately.

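### SAP 3.4 and 6.4.8 plan a norm-based T-score, with change from baseline, for the single SF-36v2 health transition item, which lies outside the only conversion the plan states

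*SAP*

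**What the plan says.** SAP 3.4 describes the instrument: "The questionnaire consists of 8 health domain scales: physical functioning (10 items), role-physical (4 items), bodily pain (2 items") and so on through mental health. The same sentence then adds reported health transition as one item, followed by the two component summaries. SAP 3.4 gives one conversion rule: "Each health domain scale raw score is transformed to 0-100 scale which can then be converted to norm-based T-scores (Mean=50, SD=10"). Protocol 8.1.3.7 ties the conversion to the domain scales in the same way and says that the SAP will hold the full derivation.

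The SAP 3.4 list of scores to be produced opens with "The following transformed norm-based T-scores will be derived: physical functioning (PF); role-physical (RP") and later runs "mental health (MH); reported health transition; physical component summary (PCS"), so health transition sits inside the T-score list. SAP 6.4.8 repeats this as "Absolute and change from baseline in the 11 SF-36v2 transformed norm-based T-scores (covering 8 domains, health transition and 2 components"). It asks for absolute values and change from baseline under SAP 5.2.1, that is number of observations, mean, standard deviation, median and range. The visits are Weeks 16 and 26 for Cohorts 1 and 2, and Weeks 16, 24 and 32 for Cohort 3.

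The endpoint in Protocol 3 and SAP 2.2 is change from baseline in the SF-36v2 subscales and summary scores. It is tertiary and has no estimand. SAP 2.1 declares no modification of the protocol's analysis plan.

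**The concern.** The plan instructs programming to produce a T-score for an item that its stated rule does not reach. For this item the SAP gives no 0-100 transformation, no norm mean or standard deviation, and no conversion table. If a number is nevertheless printed in a table headed as norm-based T-scores, a reader will take it to lie on the scale with mean 50 and standard deviation 10, and nothing in the SAP supports that reading.

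The choice of summary is a second difficulty. An item called reported health transition is, by its name, a report of change. A change from baseline in such an item is a difference between two reports of change, and its mean and standard deviation have no obvious interpretation. The output also goes beyond the protocol endpoint, because a lone item outside the domains and the component summaries is neither a subscale nor a summary score.

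**Working it through.** No sample-size or error-rate calculation applies. The check is a count, followed by a comparison of the sections.

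**Inputs (SAP 3.4).** Items per domain scale: PF 10, RP 4, BP 2, GH 5, VT 4, SF 2, RE 3, MH 5. Health transition: 1 item. Component summaries: 2 (PCS and MCS). Questionnaire length: 36 items.

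**Step 1: reproduce the plan's figure.** 8 domains + 1 health transition + 2 components = 11 scores. This matches SAP 6.4.8.

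**Step 2: place the item.** Number of named domain scales = 8. Items in them: 10 + 4 + 2 + 5 + 4 + 2 + 3 + 5 = 35. Items left over: 36 - 35 = 1, which is health transition. The eight domains are complete without it.

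**Step 3: compare with the rule and the endpoint.**

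| Score | Count | Domain scale (stated conversion applies) | Subscale or summary score (protocol endpoint) |
|---|---|---|---|
| PF, RP, BP, GH, VT, SF, RE, MH | 8 | yes | yes |
| PCS, MCS | 2 | no | yes |
| Health transition | 1 | no | no |

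Health transition is the only one of the 11 that fails both tests. Without it the list has 8 + 2 = 10 scores.

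**Step 4: look for a derivation elsewhere.** SAP Appendices 6 and 7 give conversion tables for the two PROMIS measures, and Appendix 8 gives the IWQOL-Lite-CT algorithm. There is no SF-36v2 appendix. The SAP version history says that the SF-36 T-scores will come from in-house code drawn from publications and not from the scoring software. That code is not shown.

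**Step 5: extent.** Cohorts 1 and 2 have 9 arms and 2 post-baseline visits: 9 x 2 = 18 arm-by-visit change summaries. Cohort 3 has 4 arms and 3 visits: 4 x 3 = 12. In total, 18 + 12 = 30 change summaries are affected, with the matching absolute values. This measures how often the row is repeated, not any bias.

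**The case against.** The strongest reply is that the SAP does not claim to print every scoring detail. It relies on in-house code and cites the developer's user manual and administration guide. Neither the code nor the manuals can be seen here, and the code may handle this item separately. That stands. A reader might infer that no valid T-score exists for the item. The documents do not show this; they show only that the SAP gives no derivation.

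A second reply is that the conversion sentence, taken literally, does not cover PCS and MCS either. That also stands. It would be wrong to say that the rule itself yields 10 scores: literally it reaches 8, and the SF-36v2 documentation gap is wider than one item. Even so, PCS and MCS are summary scores named by the endpoint, and health transition is not.

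Third, the opening list in SAP 3.4 can be read as placing health transition among the domain scales. This fails, because eight scales are named without it and SAP 6.4.8 counts it apart from the domains.

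Fourth, one might cite SAP 6.4.14, where "PGI-C data will be summarized categorically by treatment group and time point for each item", as proof that the SAP treats change ratings categorically on principle. That inference is too strong. PGI-C is first collected at Week 4, so it has no baseline to subtract, and SAP 3.4 does map the PGI-S items to numbers and calculate change from baseline. PGI-C is useful only as a model for the table layout.

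Finally, the documents do not reproduce the item's wording, recall period or response options. The argument about interpreting its change from baseline therefore rests on the item's name alone.

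**Conclusion.** The point holds in a limited form. SAP 3.4 and 6.4.8 apply a norm-based T-score, continuous statistics and change from baseline to one item that the plan's own text places outside the domain scales and outside the summary scores. It does so without a derivation, although the protocol says that the SAP would supply one. This is more than missing detail, because the SAP positively names the item as a T-score and fixes how it is to be summarised.

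The size is small: 1 of 11 SF-36v2 outputs, descriptive, tertiary and without an estimand. Nothing in the primary analysis, the error rate or the sample size depends on it. The count rests only on SAP 3.4 and 6.4.8. The remark on interpretability assumes that the item is what its name says, a report of change.

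**What to change.** In SAP 3.4, remove reported health transition from the list of T-scores, leaving the 8 domains, PCS and MCS. In SAP 6.4.8, change 11 to 10 and take health transition out of the parenthesis. Add a sentence that the health transition item will be tabulated as counts and percentages of each response category by treatment group and visit, under SAP 5.2.2 and separately for Cohorts 1 and 2 combined and for Cohort 3, with no T-score and no change from baseline.

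If the sponsor holds a documented T-score conversion for this item and wishes to keep it, the SAP would have to state it, and the change-from-baseline summary would still need a justification. While the section is open, a line naming the scoring source for the domains, PCS and MCS would close the wider gap.

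The cost is the wording of two SAP sections and one table shell. No new data are needed, and the protocol endpoint stays as it is.

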6.4.9. CFB in Eating-Related Factors Daily Diary

In all cases a dataset similar to Estimand Set 1 as specified in Section 4 will be utilised.

Absolute and change from baseline in the 7-day average scores for each of the 5 individual items from the Eating-Related Factors Daily Diary will be summarized descriptively by treatment group and time point for each item separately as described in Section 5.2.1, at Weeks 4, 8, 12, 16, 22 and 26 for Cohorts 1 & 2 and at Weeks 4, 8,12, 16, 20, 24, 28 and 32 at Cohort 3 separately.

6.4.10. CFB in PGI-S at each planned clinic visit up through End of Treatment visit

In all cases a dataset similar to Estimand Set 1 as specified in Section 4will be utilised.

PGI-S will be summarized categorically by treatment group and time point for each item as described in Section 5.2.2. Shift tables will also be produced to summarise the categorical changes for each item at each post-dose time-point separately.

6.4.11. CFB in PROMIS® Fatigue

In all cases a dataset similar to Estimand Set 1 as specified in Section 4 will be utilised.

Absolute and change from baseline in the PROMIS® Fatigue T-scores will be summarized descriptively by treatment group and time point as described in Section 5.2.1, at Weeks 16 and 26 for Cohorts 1 & 2 and at Weeks 16, 24 and 32 for Cohort 3 separately.

6.4.12. CFB in PROMIS® Physical Function

In all cases a dataset similar to Estimand Set 1 as specified in Section 4 will be utilised.

Absolute and change from baseline in the PROMIS® Physical Function T-scores will be summarized descriptively by treatment group and time point as described in Section 5.2.1, at Weeks 16 and 26 for Cohorts 1 & 2 and at Weeks 16, 24 and 32 for Cohort 3 separately.

PFIZER CONFIDENTIAL DMB02-GSOP-RF02 8.0 Statistical Analysis Plan Template TMF Doc ID: 98.03 Page 42 of 61

6.4.13. CFB in IWQOL-Lite-CT©

In all cases a dataset similar to Estimand Set 1 as specified in Section 4 will be utilised.

Absolute and change from baseline for each of the 3 composite scores from the IWQOL-Lite-CT© will be separately summarized descriptively by treatment group and time point as described in Section 5.2.1, at Weeks 16 and 26 for Cohorts 1 & 2 and at Weeks 16, 24 and 32 for Cohort 3 separately.

6.4.14. PGI-C

In all cases a dataset similar to Estimand Set 1 as specified in Section 4 will be utilised.

PGI-C data will be summarized categorically by treatment group and time point for each item as described in Section 5.2.2, at Weeks 4, 16 and 26 for Cohorts 1 & 2 and at Weeks 4, 16, 24 and 32 for Cohort 3 separately.

6.5. Subset Analyses

Absolute values, percentage changes from baseline and absolute changes from baseline in body weight will be summarised descriptively by treatment group, time point and biological sex as described in Section 5.2.1. The tables will present time points as described in Section 6.1.1.1 and baseline is as defined in Section 3.

6.6. Baseline and Other Summaries and Analyses

6.6.1. Baseline Summaries

Baseline tables summarizing the following will be produced by treatment group and overall: age; gender; race; ethnicity; height; body weight; body mass index; waist circumference; waist-to-hip ratio; hip circumference; country; HbA1c; fasting plasma glucose; systolic blood pressure; diastolic blood pressure; pulse rate; total cholesterol; direct LDL cholesterol; HDL cholesterol and triglycerides. The tables should be produced separately for: (1) Cohorts 1 & 2, and (2) Cohort 3.

6.6.2. Study Conduct and Participant Disposition

Participant evaluation groups will show participant disposition for each phase of the study (screening, double blind treatment and follow-up) and will additionally show which participants were analyzed for efficacy (Estimand Set 1 and 2) as well as for safety. Frequency counts and percentages will be supplied for participant discontinuation(s) by treatment group and overall for: (1) Cohorts 1 & 2, and (2) Cohort 3 data, which will be reported in accordance with the sponsor reporting standards.

6.6.4. Concomitant Medications and Nondrug Treatments

All prior and concomitant medication(s) as well as non-drug treatment(s) will be reported according to current sponsor reporting standards.

PFIZER CONFIDENTIAL DMB02-GSOP-RF02 8.0 Statistical Analysis Plan Template TMF Doc ID: 98.03 Page 43 of 61

6.6.1. Treatment Compliance

Treatment compliance (in %) will be summarised descriptively by treatment group and overall, at time point as described in Section 5.2.1. The time points will be: the Placebo runin phase; Weeks 2, 4, 6, 8, 10, 12, 16, 18, 22 and 26 for Cohorts 1 & 2 and at Weeks 4, 8, 12, 16, 20, 24, 28 and 32 for Cohort 3 separately.

Treatment compliance is defined for each time point separately as: (actual number of IP tablets / planned number of IP tablets) × 100%.

Missing information pertaining to doses administered on site will be imputed as per Section 5.3.

6.6.2. Discontinuations

Participant discontinuations, temporary discontinuations or dose reductions due to adverse events will be detailed and summarised by treatment group and overall.

Data will be reported in accordance with the sponsor reporting standards, where an additional table summarizing participant discontinuations of IP due to adverse events for each system organ class and preferred term will be produced by treatment group and overall also.

Exploratory summaries on the time to discontinuation from the study and time to discontinuation of IP (regardless of study discontinuation or continuation) will be produced separately using Cumulative Incidence Plots as described in Section 5.2.7. For both, participants who discontinue from the study/IP will be censored at the associated discontinuation date.

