5.2.7. Cumulative Incidence Plots

Cumulative Incidence Plots will be produced based on the time to the event of interest (starting from the time of start of dosing on Day 1) for each treatment group separately and will be plotted on the same graph. This will be based on plotting the cumulative incidence function (with no competing risks), which will be presented as a % on the y-axis. No statistical testing for differences between treatment groups will be considered.

PFIZER CONFIDENTIAL DMB02-GSOP-RF02 8.0 *Statistical Analysis Plan Template* TMF Doc ID: 98.03 Page 29 of 61 Details of censoring are included in Section 6 and example SAS code is provided in Appendix 3.

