6.3.1.2. Incidence of first occurrence of adverse events of interest by week

The number and percentage of participants who experience the first occurrence of a TEAE of interest each week (up to and including the follow-up visit) will be tabulated by treatment group and week, where percentage will be defined in two ways. These will be included in the same table and produced separately for each TEAE of interest.

To calculate the percentage each week, the numerator will be the total number of participants with the TEAE of interest that was also their first post-dose occurrence of the event during that respective week. The two approaches for the denominator are: (1) the total overall number of evaluable participants in the Safety Analysis Set for the respective treatment group; and (2) the total number of participants who had not discontinued from the study prior to that respective week will be the denominator (note if a participant did discontinue from the study during that respective week they would be included in the denominator).

A figure of the percentage per week will also be produced, with week on the x-axis and a separate line for each treatment group. The percentage will represent the above definition (2) of the denominator but based on blinded data reviews this figure may be adapted or additionally produced based on definition (1). These figures will be produced separately for each TEAE of interest.

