6.3.1.5. Time to discontinuation from IP due to Gastrointestinal Disorders AEs

Exploratory summaries on the time to discontinuation from IP (regardless of study discontinuation or continuation) due to Gastrointestinal Disorders AEs (defined as based on System Organ Class) will be produced with a Cumulative Incidence Plot as described in Section 5.2.7. Participants who discontinue will be censored at the associated discontinuation date.

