Appendix 3. Traditional Statistical Methodology Details

The following SAS code is to be used as a guide for implementation.

Example SAS code for MMRM Model (strata included):

Example SAS code for Cumulative Incidence Plots:

```
proc lifetest data = dataset method=km plots=cif(test) outcif=cifatrisk intervals=0 to 20 by 2;
strata treatment;
time day*censor(1)/eventcode=0;
```

run;

NOTE: the censor variable has a value = 1 when the related time is censored and has a value = 0 when the event of interest occurs. There should be no other values available for this censored variable in this dataset (including missing values). If required, missing observations should be removed prior to analysis.

PFIZER CONFIDENTIAL DMB02-GSOP-RF02 8.0 *Statistical Analysis Plan Template* TMF Doc ID: 98.03 Page 51 of 61

Example SAS code for Proportion of Responses (with multiple imputation):

Assume the SAS dataset is in a long format. The variable 'treatment' should be coded similar to 'Placebo', 'Danuglipron 40 mg BID', 'Danuglipron 80 mg BID',... 'Danuglipron 200 mg BID', 'Danuglipron 120 mg BID (2-week titration)', 'Danuglipron 160 mg BID (2-week titration)' and 'Danuglipron 200 mg BID (2-week titration)' so that when sorted in descending order 'Placebo' comes first.

proc sort data=analysis out= analysisl;

```
by subjid time treatment strata;
```

run;

```
* Create wide dataset for multiple imputation;
proc transpose data= analysisl out=analysisw prefix=week;
by subjid treatment strata;
id time;
var cfb_log;
```

run;

* Perform multiple imputation;

proc mi data=analysisw seed=169 nimpute=20 out= analysis_mi;

class treatment strata;

fcs nbiter=10 reg(/details);

var base treatment strata week2 week4 week6 week8 week10 week12 week16 week18 week22 week26;

run;

* Determine responders and non-responders at End of Treatment for all imputed datasets; data analysis mi 26;

```
set analysis_mi;
value = week26;
if value < log(0.95) and week26 ne . then resp = 1;
if value >= log(0.95) and week26 ne . then resp = 0;
```

run;

```
* Create datasets and combine proportions;
proc freq data=analysis_mi_26;
tables imputation *dose*resp/out=prop mi outpct;
```

run;

data prop_mi_0; set prop_mi; if resp=0; keep _imputation_ treatment count; rename count=count_0; run; data prop_mi_1; set prop_mi; if resp=1;

if resp=1; keep _imputation_ treatment count; rename count=count_1;

run;

```
data prop_mi_combined;
```

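### SAP 6.6.2 (Discontinuations) censors participants on the date they discontinue in two plots whose event is discontinuation; as written, every curve stays at 0%

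*SAP*

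**What the plan says.** SAP 6.6.2, Discontinuations, follows a different section also numbered 6.6.2 (Study Conduct and Participant Disposition). It plans exploratory cumulative incidence plots for two outcomes: "time to discontinuation from the study and time to discontinuation of IP (regardless of study discontinuation or continuation"). The sentence that follows sets the censoring: "For both, participants who discontinue from the study/IP will be censored at the associated discontinuation date".

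The general method is in SAP 5.2.7, which plots a cumulative incidence function with no competing risks, by treatment group, as a percentage. It gives no censoring rule of its own: "Details of censoring are included in Section 6 and example SAS code is provided in Appendix 3". It also says "No statistical testing for differences between treatment groups will be considered".

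The sample code in Appendix 3 uses "time day*censor(1)/eventcode=0". The accompanying note says the censor variable "has a value = 1 when the related time is censored and has a value = 0 when the event of interest occurs", and that no other values should be present.

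SAP 6.3.1.5, on time to IP discontinuation due to gastrointestinal AEs, has a similar sentence: "Participants who discontinue will be censored at the associated discontinuation date".

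**The concern.** A time-to-discontinuation curve rises only when someone discontinues. If every discontinuer is censored on that date, and participants who complete have no event, nobody contributes an event. The outcome named in 6.6.2 and the coding in Appendix 3 imply that discontinuation is the event, but the sentence that actually sets the censoring says the opposite. The section also never says when participants who do not discontinue are censored.

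At stake is the SAP's planned time-to-event display of all-cause stopping in each arm. That matters to the design: Protocol 4.2 says Cohort 2 was added to characterise 2-week titration better and Cohort 3 to characterise 4-week titration, tolerability included. It also rules out downward titration, so a participant who cannot tolerate the assigned dose may have to stop dosing.

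**Working it through.** The SAP states no value for these curves, so there is no document figure to reproduce. The check applies the written rule and then the evident intention.

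**Inputs**
- Outcomes and censoring rule: SAP 6.6.2, Discontinuations.
- Quantity plotted: cumulative incidence without competing risks, SAP 5.2.7. This equals 1 minus Kaplan-Meier.
- Coding: 1 = censored, 0 = event, Appendix 3.
- Planned sizes and completers, Protocol 9.2: Cohort 1, 420 randomised and about 315 completing; Cohort 3, 112 randomised and about 84 completing.
- Planned arm sizes, Protocol 4.1 and 9.2: 67 (placebo, Cohorts 1 and 2), 60 (each 1-week arm), 34 (each 2-week arm), 16 (Cohort 3 placebo), 32 (each Cohort 3 active arm).
- End of treatment: day 182 (Cohorts 1 and 2) and day 224 (Cohort 3), from the schedules of activities.

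**Formula**

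F(t) = 1 − ∏ over event times tⱼ ≤ t of (1 − dⱼ/nⱼ), where dⱼ is the number of events at tⱼ and nⱼ the number at risk.

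**1. Rule as written.** Every discontinuer has censor = 1, and completers have no event. So every dⱼ = 0, the product is 1, and F(t) = 1 − 1 = 0 at all times. This does not depend on arm size or rate. Running it for all five arm sizes, with assumed discontinuation rates of 10%, 25%, 40% and 60%, gave 0.000 each time.

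**2. Discontinuation as the event.** Completers are censored at day 182 or 224. Nobody is censored before the last event, so the final value is simply discontinuers divided by participants.
- Cohort 1: 420 − 315 = 105; 105/420 = 25.0%.
- Cohort 3: 112 − 84 = 28; 28/112 = 25.0%.
- By arm at 25%, rounded to whole participants:

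| Arm | n | Discontinue | As written | Discontinuation as event |
|---|---|---|---|---|
| Placebo, Cohorts 1 and 2 | 67 | 17 | 0% | 25.4% |
| 1-week arm | 60 | 15 | 0% | 25.0% |
| 2-week arm | 34 | 8 | 0% | 23.5% |
| Placebo, Cohort 3 | 16 | 4 | 0% | 25.0% |
| Active arm, Cohort 3 | 32 | 8 | 0% | 25.0% |

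Over the assumed 10% to 60% range the final values run from 8.8% (3/34) to 62.5% (10/16), against 0% throughout as written.

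**3. Participants affected.** A flat 25% of the planned 581 is 0.25 × 581 = 145.25, so about 145 participants would have their event coded as censored in the study plot.

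**4. Can another reading rescue the sentence?** It might be meant crosswise: study discontinuers censored in the IP plot, and IP discontinuers censored in the study plot. The words 'for both' and 'associated' do not say that. The first half would conflict with the section's own statement that IP discontinuation counts regardless of study status, and with Protocol 7.2, under which withdrawal from the study also ends study intervention. The second half would conflict with Protocol 7.1, under which participants who stop IP stay in the study and so remain at risk of leaving it.

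**5. Related wording.** In SAP 6.3.1.4 the event is an AE, so censoring at discontinuation is coherent. SAP 6.3.1.5 is coherent if its discontinuers are those who stop IP for reasons other than gastrointestinal AEs, but it does not say so.

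**The case against.** The strongest reply is that this is a drafting slip, perhaps carried over from 6.3.1.4, and that no competent programmer would code it literally. The outcome is named one sentence earlier, the Appendix 3 code is offered only as a guide, and an empty curve would be noticed. The information is also partly available elsewhere. The other section numbered 6.6.2 tabulates discontinuations by arm. SAP 6.3.1.5 plots IP discontinuation due to gastrointestinal AEs. Weekly denominators partly show retention; in SAP 6.3.1.2, for example, "the total number of participants who had not discontinued from the study prior to that respective week will be the denominator" is one of the two used. The plots are exploratory, and the 25% comes from the sample-size assumptions rather than from any statement about these curves.

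Most of this stands as a limit on importance. It does not remove the error. SAP 5.2.7 sends the programmer to this sentence for the rule, and the rule is wrong. Reversing the coding by common sense still leaves open when participants who do not discontinue are censored. The two plots need different answers, because participants off drug stay in the study.

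**Conclusion.** The concern holds. The censoring rule for both plots contradicts their outcome and, as written, produces zero events and a 0% curve in every arm. That result rests on the text alone and needs no assumed rate.

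The comparison value of about 25% rests on the planned drop-out rate in Protocol 9.2. It is illustrative for the study plot; for the IP plot it is an assumption, because the documents give no separate planned rate for stopping IP.

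The practical effect is confined to two exploratory displays. No primary or secondary efficacy estimate changes. The sentence should nevertheless be corrected, because it defeats the output it governs and SAP 7.2 applies this SAP's methodology to interim analyses as well.

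**What to change.** In SAP 6.6.2, Discontinuations, replace the censoring sentence with: *Discontinuation (from the study or of IP, respectively) is the event on its date (censor = 0); participants who do not discontinue are censored at last study visit (study plot) or last dose (IP plot).* Last visit and last dose are proposals, since the documents prescribe neither. Last visit includes follow-up, whereas the check above censored completers at end of treatment; for the same 105 and 28 discontinuers the final value is unchanged.

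In SAP 6.3.1.5, add one line: IP discontinuation due to a gastrointestinal AE is the event, and the censoring applies to participants who stop IP for other reasons. The same last-dose rule can serve for those who complete treatment.

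The cost is two sentences of SAP text, with no new data and no change to the two-value coding in Appendix 3. Separately, the sample code there requests `cif(test)`, which sits poorly with the statement in 5.2.7 that no testing will be considered; that option could be dropped in the same edit.
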